5.2 Study Product Formulation and Preparation

5.2.1 XFBD: Supplied as 10 g granules in plastic packaging. Store at controlled room temperature 20-25°C.

5.2.2 Placebo: Supplied as 10 g granules in plastic packaging visually matching the XFBD. Store at controlled room temperature 20-25°C.

5.3 Pharmacy: Product Supply, Distribution, and Accountability

5.3.1 Study Product Acquisition/Distribution

XFDB are manufactured by Tianjin Tasly Pharmaceutical Co., LTD (<https://www.tasly.com>), a well-established TCM research and manufacture center to integrate technology and innovation to update the practice of TCM for human health.

5.3.2 Study Product Accountability

A dedicated study team member will operate an accountability and dispensing log. The drug will be secured and stored in a safe location.

5.4 Concomitant Medications

Whenever a concomitant medication is initiated or a dose changed, investigators must review the concomitant medication's and study agent's most recent package insert, Investigator's Brochure to obtain the most current information on drug interactions, contraindications, and precautions.

5.4.1 Prohibited Medications

5.4.1.1 Non-study TCM prescriptions

5.4.1.2 Ephedrine and pseudoephedrine products

5.4.1.3 MAO inhibitors, ergot derivatives, digoxin, Artemether, Lumefantrine

5.4.1.4 Strong inducers or inhibitors of CYP3A and other CYP enzymes, including apalutamide, carbamazepine, enzalutamide, mitotane, phenytoin, rifampin, St. John's wort, boceprevir, cobicistat, danoprevir

and ritonavir, elvitegravir and ritonavir, grapefruit juice, indinavir and ritonavir, itraconazole, ketoconazole, lopinavir and ritonavir, paritaprevir and ritonavir and (ombitasvir and/or dasabuvir), posaconazole, ritonavir, saquinavir and ritonavir, telaprevir, tipranavir and ritonavir, telithromycin, troleandomycin, voriconazole, bupropion, fluoxetine, paroxetine, quinidine, terbinafine, fluconazole, fluvoxamine, ticlopidine, ciprofloxacin, enoxacin, gemfibrozil, clarithromycin, idelalisib, nefazodone, nefnavir, tizanidine, repaglinide, tolbutamide, s-warfarin, lansoprazole, omeprazole, desipramine, dextromethorphan, nebivolol, midazolam, triazolam, clopidogrel, phenobarbital, theophylline

5.4.2 Potential Drug-Drug Interactions

Medicinal	Latin	Drug-Drug Interactions (DDI)	Special Consideration
麻黄	Ephedrae Herba	
Do Not Use Together:
 
 MAO Inhibitors - ephedrae herba's main component is ephedrine and MAO inhibitors may enhance the hypertensive effect of ephedrine. Ergot Derivatives - ephedrae herba's main component is ephedrine and ergot derivatives may enhance the hypertensive effect of ephedrine Inhalation Anesthetics - ephedrae herba's main component is ephedrine and inhalation anesthetics may sensitize the heart to arrhythmic actions of ephedrine. Digoxin^a – ephedrae herba's main component is ephedrine and digoxin may sensitize the heart to arrhythmic actions of ephedrine 
Potential DDIs:
 
 Calcium channel blocker Angiotensin II Antagonists Alpha-/Beta-blockers Alpha-/Beta-agonists Guanethidine (NE blocker) Methyldopa Clonidine Theophylline Phenobarbital 	Renal failure – ephedrine is mostly excreted renally
苦杏仁	Armeniacae Semen Amarum	Potential DDIs: 
 CNS depressants (benzodiazepines, barbiturates) 	
生石膏	Gypsum Fibrosum	Potential DDIs: 
 Tetracyclines Levodopa Digoxin 	
苍术	Atractylodis Rhizoma		Increases CYP3A4 activity (69)
广藿香	Pogostemonis Herba		
青蒿	Artemisiae Annuae Herba	
Do Not Use Together:
 
 Artemether – enhances toxic effect of Artemisinin Lumefantrine – enhances toxic effect of Lumefantrine 
Potential DDIs:
 
 Dapsone 	Increases CYP3A4 and 2B6 activity

马鞭草	Verbena Herba		
虎杖	Polygoni Cuspidati Rhizoma et Radix	Zidovudine – decreases clearance, increases toxicity (68)	Long term, large dosage can reduce synthesis of coagulation factors in the liver
芦根	Phragmitis Rhizoma		
葶苈子	Descurainiae Semen		
化橘红	Citri Grandis Exocarpium		Inhibits CYP3A4, 1A2 (70)
甘草	Glycyrrhizae Radix et Rhizoma	Potential DDIs: (68) 
 • Diuretics (other than potassium-sparing ones) • Digoxin • Aspirin • Reserpine • Glucocorticoid • Sulfonamides • Theophylline 	Medications metabolized by the liver – induces liver enzymes and can accelerate the metabolism of liver metabolized drugs Induces CYP3A4, 2B1, 1A2

^a This has been theorized due to the mechanism of action for ephedrae herba and digoxin. However, no clinical study has been conducted to confirm the interaction.

Drugs that are listed above as “Do Not Use Together” are prohibited and patients receiving such agents are ineligible for study participation. Given the short duration of administration of the XFBD patients receiving drugs listed as “Potential DDIs” are eligible, but, in the event of adverse events, such a DDI will be considered by the medical monitor in consultation with the patients’ health care provider.

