4.3.4 Receiving the following classes of agents found in 5.4.1. Prohibited Medications

4.3.5 Use of drugs for anti-SARS-CoV-2 treatment including remdesivir, baricitinib, lopinavir/ritonavir fixed dose combination, ribavirin, chloroquine, hydroxychloroquine, and azithromycin, dexamethasone, bamlanivimab, casirivimab plus imdevimab convalescent plasma, or participation in a clinical trial involving any of these drugs whether for treatment or prophylaxis.

4.3.6 Participating in a study where co-enrollment is not allowed.

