9 CRITERIA FOR DISCONTINUATION

9.1 Permanent and Premature Treatment Discontinuation

- Drug-related toxicity or allergic reaction (see [section 8.0](#)).
- Requirement for prohibited concomitant medications (see [section 5.4.1](#)).
- Request by participant to terminate treatment.
NOTE: The reason for treatment discontinuation should be documented (e.g. concern for AE, lack of efficacy, or other reason).
- Clinical reasons believed life threatening by the physician, even if not addressed in the [section 8.0](#) of the protocol.

9.2 *Premature Study Discontinuation*

- 9.2.1 Failure to take the first dose (directly observed/confirmed over telephone) of study treatment within 2 days of study entry.
- 9.2.2 Request by the participant to withdraw consent.
- 9.2.3 Request of the health care provider if she or he thinks the study is no longer in the best interest of the participant.
- 9.2.4 At the discretion of the IRB/EC, FDA, NIAID, Office for Human Research Protections (OHRP), other government agencies as part of their duties, investigator, or industry supporter.

In the event that a participant prematurely discontinues from the study, unless they have withdrawn consent, sites will attempt to obtain information regarding vital status (including date last seen alive, hospitalization, date of death, and primary cause of death) from other sources (such as family members, other designated contacts, or clinic records) per [section 6.2.15](#).

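### Section 5.4.2 calls users of Potential DDIs drugs eligible without exempting drugs that 5.4.1 prohibits, so theophylline, phenobarbital and, read literally, digoxin get contradictory eligibility answers.

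*Combined protocol and SAP*

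**What the plan says.** Section 5.4.1 is the list of prohibited medications. Item 5.4.1.4, headed as strong inducers or inhibitors of CYP enzymes, ends with "triazolam, clopidogrel, phenobarbital, theophylline". Item 5.4.1.3 reads "MAO inhibitors, ergot derivatives, digoxin, Artemether, Lumefantrine".

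Two other rules point to that list. Exclusion 4.3.4 is worded "Receiving the following classes of agents found in 5.4.1. Prohibited Medications". Section 9.1 gives "Requirement for prohibited concomitant medications" as a ground for permanent treatment discontinuation and refers to 5.4.1. Neither mentions 5.4.2.

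Section 5.4.2 sorts interacting drugs, herb by herb, mainly into Do Not Use Together and Potential DDIs. The Potential DDIs entry for Ephedrae Herba includes "Guanethidine (NE blocker) Methyldopa Clonidine Theophylline Phenobarbital". The one for Glycyrrhizae Radix et Rhizoma includes "Glucocorticoid • Sulfonamides • Theophylline". The paragraph after the table makes users of Do Not Use Together drugs ineligible. It then says that, because dosing is short, "patients receiving drugs listed as “Potential DDIs” are eligible". If adverse events occur, the medical monitor is to consider the interaction.

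**The concern.** The closing paragraph of 5.4.2 is written as an eligibility rule. It has one sentence for each category of drug, gives a reason for the second, and says how those patients are to be handled. A study coordinator who looks up theophylline or phenobarbital in the table finds only a Potential DDIs entry and is then told that the patient may enter. The same patient is excluded under 4.3.4. Nothing in the protocol says which text prevails.

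At stake is consistent application of a drug-safety exclusion in a pilot that screens remotely, assesses adverse events remotely, and has the safety profile among its primary objectives. A patient enrolled on the strength of 5.4.2 would meet a 9.1 ground for stopping treatment from the outset.

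**Working it through.** No formula applies to the contradiction itself, so the check sets the texts side by side. Inputs: the named drugs in 5.4.1, the table and closing paragraph of 5.4.2, exclusion 4.3.4, and 9.1.

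Step 1. Find the drugs named individually both in 5.4.1 and under Potential DDIs. There are three:

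| Drug | Prohibited in | Potential DDIs entries | Do Not Use Together entries |
|---|---|---|---|
| Theophylline | 5.4.1.4 | 2 (Ephedrae Herba, Glycyrrhizae) | 0 |
| Phenobarbital | 5.4.1.4 | 1 (Ephedrae Herba) | 0 |
| Digoxin | 5.4.1.3 | 2 (Gypsum Fibrosum, Glycyrrhizae) | 1 (Ephedrae Herba) |

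Step 2. Apply 4.3.4. All three drugs are in 5.4.1, so users of any of them are excluded.

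Step 3. Apply the closing paragraph of 5.4.2 as written. Theophylline and phenobarbital have no Do Not Use Together entry, so only the second sentence reaches them and the answer is eligible. Digoxin falls under both sentences, so the answer is ineligible by one and eligible by the other.

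Step 4. Look for a precedence rule. Neither section 4.3 nor sections 5.4 or 9.1 says that 5.4.1 overrides 5.4.2, or the reverse. Digoxin comes out as prohibited only if the stricter of two statements is allowed to win. That is sensible, but it is a convention the reader has to supply.

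Step 5. Follow a patient enrolled through 5.4.2. Section 3 replaces only participants who do not start treatment. Under 6.2.17 those who stop treatment early remain on study, and under 10.6 anyone with a confirmed first dose is in the modified intention-to-treat set. This is ordinary handling of an ineligible patient found after dosing and is not a fault. It means only that the place to prevent the error is screening.

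**The case against.** The strongest reply is that eligibility is already determined. Any one exclusion criterion is enough, 4.3.4 is in the formal list, and both drugs are named in the section it cites. On this view, eligible in 5.4.2 means only that the herb interaction does not itself bar the patient. It cannot mean eligible whatever else applies: someone on a calcium channel blocker, also a Potential DDIs entry, is still excluded by 4.3.9 if they have known kidney disease. The medication history in 6.2.20 records drug names, so a screener can apply 4.3.4.

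Most of this stands. It shows that 4.3.4 should govern and that a careful site would probably exclude these patients. It does not remove the contradiction. The kidney-disease case turns on a separate characteristic of the patient, whereas here two lists give opposite answers about the same drug. For digoxin, the two sentences of one paragraph disagree with each other.

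Three stronger readings are tempting and are not supported:

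- A reader might infer that the protocol admits these patients or leaves their status open. It does not, because 4.3.4 excludes them.
- A reader might infer that wrongful enrolment is likely. The documents give no rate of use. Purely as an assumption, if 0.1% to 1% of otherwise eligible patients took theophylline or phenobarbital, the chance of at least one user among 60 would run from 1 − 0.999^60 = 5.8% to 1 − 0.99^60 = 45.3%. Nothing in the documents anchors that range. It is also only an upper bound on wrongful enrolment, since it supposes that the screener always follows 5.4.2 over 4.3.4.
- A reader might extend the point to drug classes, such as midazolam and triazolam in 5.4.1.4 against "CNS depressants (benzodiazepines, barbiturates" in the table. That relies on class memberships the protocol does not state, and the point does not need it.

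**Conclusion.** The point holds as an internal contradiction with a minor effect. By name, two drugs (theophylline and phenobarbital) are excluded under 4.3.4 and called eligible by 5.4.2, and a third (digoxin) is called both ineligible and eligible within 5.4.2. The practical risk is that a screener who works from the interaction table enrols a patient whom the protocol means to keep out. How often that might happen cannot be estimated from the documents. No sample size, endpoint, estimate or analysis depends on it. The conclusion rests on the text alone, together with the judgement that a formal exclusion criterion outranks a statement in the concomitant-medication section. The change is still worth making because it concerns participant safety and costs almost nothing.

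**What to change.** Amend the eligibility sentence after the 5.4.2 table along these lines: users of a drug in the Potential DDIs category may enter the study unless that drug is also prohibited under 5.4.1 or has a Do Not Use Together entry, in which case the prohibition takes precedence.

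This settles all three drugs at once and leaves the prohibited list and the table as they are. Deleting theophylline and phenobarbital from 5.4.1.4 would also end their contradiction, but it would loosen a safety exclusion and leave the digoxin entries unresolved.

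The cost is one sentence in an amendment. No patient loses eligibility through the 5.4.1 clause, because 4.3.4 already excludes users of these drugs, and 5.4.2 itself already bars users of Do Not Use Together drugs. Data collection and analysis do not change.

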6. CLINICAL AND LABORATORY EVALUATIONS

6.1 Schedule of Evaluations (SOE)

Table 6.1

Evaluations	Screening ^a	Entry	Post Entry Evaluation									Premature Study Discontinuation		
			Day 0	Day 1	Day 3	Day 7	Day 14	Day 21	Day 28	Day 42	Week 12			
Visit Location			Remote											
Informed Consent	X													
Documentation of Positive SARS-CoV-2 Molecular Test	X													
COVID-19 Symptom Screen	X													
Medical/Medication History Form	X													
Identify health care providers	X													
Identify Secondary Contacts ^b	X													
Study Kit Dispensed ^c		X												
Self-administration of Study Agent PO BID		X	X	X	X	X								
Confirmation of First Dose		X												
Distribution of Symptom Self Reporting Application		X												
Daily study questions via study App or phone			X	X	X	X	X					X		
Adverse Events Tracking					X	X	X	X	X					
Review of Adherence				X	X	X						X		
At home specimen collection for SARS-CoV-2 viral RNA testing			X		X	X								
Study Endpoint Determination			X	X	X	X	X	X	X	X ^d		X		

^a Participants must begin study treatment within 96 hours of onset of their first symptom. ^b To enable updating data in the event the participant is hospitalized or dies. ^c Study kit contains: Copy of informed consent, Information about the study, Instructions on study procedures, QR Code and Internet link for Symptom Self Reporting Application, Study agent, Instructions on what to do if they have worsening symptoms/become hospitalized ^d Direct contact and medical record review.

6.2 Study Enrollment Procedures

6.2.1 Recruitment and Informed Consent

This trial will recruit study participants through community health care sites and programs (Appendix 2 that lists the sites) that are performing SARS-CoV-2 testing of symptomatic patients.

It is expected that potential participants will be referred to this trial immediately upon SARS-CoV-2 diagnosis by FDA approved nucleic acid testing.

At the time of disclosure of the SARS-CoV-2 positive test results by the health care provider, the patient will be informed about the study opportunity and provided with the study contact information. If agreed to by the patient, the health care provider will directly provide the trial coordinating office with the patients contact information. In this case, the health care provider will document in the patients EHR their consent to provide the trial staff with their contact information.

The trial office will operate from 8:00 AM to 6 PM seven days per week to accept calls from these SARS-CoV-2 positive patients inquiring about the study. For patients, whose contact information is provided by their health care providers, contact will be made the same day.

The study is designed to minimize in-person contact between participants and study staff. The informed consent process, screening, and randomization are performed remotely.

If the patient signs up for COVID-19 testing through the Los Angeles county website, the patient can consent to being contacted by clinical trial study coordinators (Appendix VII). If a consenting patient tests positive, the initial recruitment telephone or video conference call will be made.

At the initial recruitment telephone or video conference encounter the script information will be read to the study participant in their primary language (English, Spanish, Cantonese, Mandarin). Potential participants expressing interest will be provided with the electronic informed consent in their primary language, California Experimental Subjects Bill of Rights and an authorization for medical information (HIPAA) as a digital document. Potential participants will be informed that entry to the study must be within 96 hours of symptom onset.

At this initial recruitment telephone or video conference encounter with the potential participants verbal consent the screening eligibility assessment may be completed. If potential participants wish to review and sign the informed consent first, the screening and eligibility assessment can be completed at the next telephone or video conference encounter.

6.2.2 Informed Consent Process - Remote

Potential participants will be provided with the electronic informed consent (eIC), California Experimental Subjects Bill of Rights and HIPAA agreement as digital documents.

The informed consent process is done using videoconferencing or telephone between the study coordinator (delegated by the principal investigator) and includes discussion of the California Experimental Subjects Bill of Rights, discussion of the informed consent using the text of the approved informed consent as the text for the discussion of the informed consent and an explanation of the HIPAA authorization. The consent process and documentation is consistent with 21 CFR part 11 in addition to parts 50, and 56, and 45 CFR 46.

The research participant will be given the opportunity to discuss with their family and others including their health care providers. All questions raised by the potential participant will be answered by the study

coordinator. Participants who have reviewed the eIC, and had all questions addressed, volunteer to participate will use the electronic signature of the eIC to document. An official form of identification, such as a digital image of the patient's birth certificate, government-issued passport or a driver's license will be obtained to verify the identity of the patient. They will receive a digital signed copy of the eIC via email and a physical unsigned blank.

6.2.3 Screening Visit - Remote

For potential participants who elect to complete the screening and eligibility assessment after the informed consent process has been completed, this screening telephone/telemedicine visit will be conducted.

6.2.4 Documentation from a health care/provider encounter - Remote

If the screening evaluation indicates either an encounter with a health care provider or symptoms greater than mild COVID-19 with shortness of breath (see table 3 above), documentation from the health care provider encounter will be obtained. This must include vital signs, SpO2 to permit classification of COVID-19 as mild or moderate which are eligible or greater than moderate which are not eligible for participation. The participants consent and HIPAA authorization will be required to obtain this health information from the provider.

6.2.5 Screen Failures

In addition to data being collected on participants who enroll into the study, demographic, clinical, and laboratory data on screening failures will be captured including the reason for screen failure.

6.2.6 Registration and Randomization

When the potential research participant signs, the documents using the digital documents and the screening and eligibility assessment confirms eligibility, the research participant will be registered and randomized.

6.2.7 Study Entry Visit (Day 0) - Remote

Upon receipt of the signed eIC, HIPAA authorization, and health information if required for greater than mild COVID-19, and completion of the screening and eligibility assessment for those eligible the study entry remote visit will be conducted.

Screening and entry remote visits may be combined for mild COVID-19, but moderate COVID-19 will require separate visits so the medical information from the health provider can be reviewed to ensure they qualify as moderate COVID-19. The study entry visit is a remote contact telephone contact or video conference encounter. Participants must begin study treatment within 96 hours of the onset of symptoms.

Participants will be informed that they are eligible.

6.2.8 Study Kit Dispensed

The kit will include:

- 6.1.1.1 Study agent
- 6.1.1.2 Blank copy of informed consent and HIPPA authorization
- 6.1.1.3 Information about the study
- 6.1.1.4 Instructions on study procedures
- 6.1.1.5 3 sets of COVID-19 Test Home Collections Kits ^a
- 6.1.1.6 QR Code and Internet link for Symptom Self Reporting Application (Appendix VI)
- 6.1.1.7 Instructions on what to do if they have worsening symptoms/become hospitalized

^aAn FDA Emergency Use Authorization approved home kit solution such as the Fulgent COVID-19 by RT-PCR test will be used. (73) It is a nasal swab collection followed by a FDA EUA approved PCR test conducted in the CLIA/CAP laboratory of Fulgent Genomics, determining the presence or absence of RNA from SARS-CoV-2 virus. The kit will include instructions, a swab and tube, alcohol prep pad, kit ID stickers, biohazard bag, absorbent sheet, return label, return box, and return envelope. The participant will be provided sample collection instructions and how to return the sample both in an illustrated print out and video. (74) The print outs are available in the supplemental materials.

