1. HYPOTHESIS AND STUDY OBJECTIVES

1.1. *Hypothesis*

- 1.1.1. Xuanfei Baidiu granules (XFBD) will prevent hospitalization and death in persons with symptomatic SARS-CoV-2 infection.

1.2. *Primary Objective*

- 1.2.1. To document the feasibility of recruitment through community setting by assessment of the number of positive cases identified per week.
- 1.2.2. To document the proportion of patients who agree to participate as measured by enrollment and randomization.
- 1.2.3. To document the treatment emergent side effects and safety profile of the XFBD and placebo.
- 1.2.4. To document the rate of hospitalization or death within 42 days of enrollment in the XFBD and placebo treated groups.

1.3. *Secondary Objectives*

- 1.3.1. To document the effect of XFBD on Symptom Severity Score within 28 days of enrollment in the XFBD and placebo treatment.
- 1.3.2. To document the proportion of patients who are compliant taking greater than 90% of the test substance as measured by self-report
- 1.3.3. To document the proportion of patients who comply with symptom monitoring.
- 1.3.4. To document the proportion of patients who comply with repeated clinical testing.
- 1.3.5. To document the hospital-free days from enrollment to 42 days (number of days patient not in hospital).
- 1.3.6. To document cumulative incidence of serious adverse events, and adverse events leading to early discontinuation of XFBD or placebo.
- 1.3.7. To document cumulative incidence of grade 3 and 4 adverse events.
- 1.3.8. To obtain levels (detectable versus not detectable, and continuous on log10 scale) of SARS-CoV-2 RNA from nasal swabs at approximately days 1, 7 and 14 among a subset.

1.4. *Exploratory Objectives*

- 1.4.1. To document the rate of subjects tested as negative for SARS-CoV-2 at day 14.
- 1.4.2. To document the rate of housemate infection.
- 1.4.3. To document if XFBD changed the severity and duration of self-reported symptom experience of COVID-19.

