10.2.2 Secondary Outcome Measures

- 10.2.2.1 To document the effect of XFBD on Symptom Severity Score within 28 days of

study entry.

- 10.2.2.2 To document the proportion of patients who are compliant taking greater than 90% of the test substance as measured by self-report
- 10.2.2.3 To document the proportion of patients who comply with symptom monitoring.
- 10.2.2.4 To document the proportion of patients who comply with repeated clinical testing.
- 10.2.2.5 To document cumulative incidence of serious adverse events, and adverse events leading to early discontinuation of XFBD or placebo.
- 10.2.2.6 To document cumulative incidence of grade 3 and 4 adverse events.
- 10.2.2.7 To obtain levels (detectable versus not detectable, and continuous on log10 scale) of SARS-CoV-2 RNA from nasal swabs at approximately days 1, 7 and 14 among a subset.

10.3 *Randomization and Stratification*

[figure not shown]
Eligible participants will be randomized using a 1:1 ratio to each of the study arms. Housemates of participants previously enrolled will be independently randomized so that housemates will not be clustered within treatment group.

Randomization will be stratified by “high” vs “low” risk of severe disease, where “high” risk is defined by any of the following: age ≥ 60 years, or having any of a number of conditions, as described in section 3.3.

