10.6.2 Secondary Outcomes

Symptom severity scores will be determined from the COVID-19 symptom PROs reported daily by participants. Each symptom is rated by the participant on a scale from 0-4. Although the seriousness of the symptoms are not equal, summing the individual symptom ratings will give a rough measure of the participant's disease severity. These daily symptom severity scores will be summed over the 28-day period using area under the curve (AUC). Comparisons of this AUC, as well as weekly symptom severity scores, by age, race/ethnicity, gender, risk group and assigned treatment will be performed using Wilcoxon rank sum tests. For this, and all comparisons by demographic or treatment variables, the results will be considered for planning purposes only. Secondary outcomes 2, 3, and 4 involve compliance proportions and will be documented in total and compared by demographic and treatment variables using Fisher exact tests. Secondary outcomes 5, 6, and 7 involve event rates which will be calculated in total and compared by demographic and treatment variables using negative binomial regression. Detectable versus not detectable SARS-CoV-2 RNA from nasal swabs at days 7 and 14 will be compared by demographic and treatment variables using Fisher exact tests, and continuous measures of SARS-CoV-2 RNA (on log10 scale) will be assessed for normality and tested using t-tests or Wilcoxon rank sum tests, as appropriate.

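### The planned log10 viral RNA level cannot come from the presence/absence home test the protocol describes; the detectable/not detectable half can

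*Combined protocol and SAP*

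**What the plan says.** Secondary objective 1.3.8 is to obtain "levels (detectable versus not detectable, and continuous on log10 scale) of SARS-CoV-2 RNA from nasal swabs" at about days 1, 7 and 14 in a subset. Section 10.2.2.7 repeats this as an outcome measure.

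Section 10.6.2 analyses the two forms separately. The binary form at days 7 and 14 gets Fisher exact tests. For the other form, "continuous measures of SARS-CoV-2 RNA (on log10 scale) will be assessed for normality and tested using t-tests or Wilcoxon rank sum tests, as appropriate".

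The schedule in section 6.1 has one line for these specimens: "At home specimen collection for SARS-CoV-2 viral RNA testing". Footnote a of section 6.2.8 describes the assay. An "FDA Emergency Use Authorization approved home kit solution such as the Fulgent COVID-19 by RT-PCR test will be used", and the laboratory test is described as "determining the presence or absence of RNA from SARS-CoV-2 virus". Sections 6.2.9, 6.2.11 and 6.2.12 use the same home kit for the three swabs.

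**The concern.** The outcome asks for a quantity, and the assay text offers a yes/no result. If the trial runs as described, there is nothing to put on a log10 scale, and the planned test of the continuous form has no data. This has to be settled before samples are run, because a laboratory contracted for positive/negative reports may not be able to supply values afterwards.

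A second gap sits behind the first. Even with a quantitative readout, a negative swab has no log10 value, and section 10.6.2 does not say how it enters the analysis. The protocol plainly expects negatives: it tests the binary form at days 7 and 14, and objective 1.4.1 is the rate of negative tests at day 14. A t-test would need either an imputed number or the removal of those participants. Removing them would leave a comparison among people still shedding, a group defined after randomisation that treatment could affect.

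**Working it through.** The documents give no sample size, SD, effect or power for this outcome, so there is no figure of the plan's own to reproduce. The check is a comparison of the text, followed by two illustrations on stated assumptions.

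**Step 1: what each half needs, and what is provided.**

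- Binary half (1.3.8, 10.2.2.7) and objective 1.4.1: need positive or negative per swab. Footnote a of 6.2.8 provides this, and 10.6.2 has a matching test for the binary half. Deliverable.
- Continuous half (1.3.8, 10.2.2.7): needs a level per swab. Nothing in 6.1, 6.2.8 to 6.2.12, 10.2.2 or 10.6.2 mentions quantitative PCR, cycle-threshold values, a calibration, a unit, or a limit of detection or quantification. Not deliverable from the assay as described.
- Rule for negatives in the continuous analysis: none in 10.6.2.

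**Step 2: how much the missing rule could matter.** These assumptions are not in the documents: detected values average 4.0 log10 copies in both arms, the limit of detection (LOD) is 100 copies, and non-detects are 40% on placebo and 60% on XFBD. If non-detects are coded as c, an arm's mean is q × c + (1 − q) × 4.0, where q is its non-detect share. The difference, placebo minus XFBD, is therefore (0.60 − 0.40) × (4.0 − c).

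- Set to 0: 0.20 × 4.0 = 0.80.
- Set to half the LOD, log10(50) = 1.70: 0.20 × 2.30 = 0.46.
- Set to the LOD, log10(100) = 2: 0.20 × 2 = 0.40.
- Dropped: 4.0 − 4.0 = 0.00. If all 30 per arm are swabbed, 30 × 0.60 = 18 and 30 × 0.40 = 12 values are left.

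Non-detect shares of 30% versus 50%, or 50% versus 70%, give the same four differences, because only the 20-point gap enters the formula.

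**Step 3: how many non-detects to expect.** The nearest figures are in the Wuhan Experience paragraph of section 2.2: 250 of 273 XFBD-treated patients reached two consecutive negative tests, at 11.02 ± 3.59 days. Assume a normal distribution.

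- If ±3.59 is an SD, day 14: Φ((14 − 11.02)/3.59) = Φ(0.83) = 0.797, and × 250/273 = 0.73. Day 7: Φ((7 − 11.02)/3.59) = Φ(−1.12) = 0.131, and × 250/273 = 0.12.
- The paragraph attaches a 95% label to the ± figure. If 3.59 is 1.96 SDs, the SD is 1.83. Then day 14 is Φ(1.63) = 0.948, × 250/273 = 0.87, and day 7 is Φ(−2.19) = 0.014, × 250/273 = 0.01.
- Section 2.1 reports a quarter of persons still shedding at 3 weeks, so about 75% negative by then and presumably fewer at 2 weeks.

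The day 14 share could be large, but the documents do not fix it. On the Wuhan figures the day 7 share is small.

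**The case against.** The best defence has four parts.

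1. The kit is named only as an example and the method is RT-PCR, so a quantitative readout is not ruled out. This stands, and it is why the finding concerns the assay as described, not what is technically possible. But no sentence in the plan arranges for such a readout.

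2. Section 10.6.2 already offers the Wilcoxon test. A block of non-detects coded at one value would be expected to fail the normality check, and Wilcoxon can rank them tied lowest with no imputed number. This stands in part. What is missing is the sentence assigning that rank. Without it the normality check depends on how negatives are coded: if they are left out, the remaining values may pass and lead to the t-test.

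3. A reader might infer that an effective treatment would remove its own successes from the analysis. The documents do not support that. No passage says negatives will be dropped, and the Fisher tests count converters as not detectable, so they remain in the analysis of this outcome.

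4. A reader might take the 73% above and conclude that about 8 per arm (30 × 0.27) would have a day 14 value. That is not supported either. The source is an uncontrolled, XFBD-treated hospital group whose starting point for the clock is not stated. It measures time to two consecutive negatives, not the result of one home swab. Using it for both arms gives placebo the treated rate, and it assumes all 30 per arm are swabbed although the outcome is limited to a subset of unstated size.

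**Conclusion.** The outcome and the assay contradict each other on the continuous half. As written, the trial can report detectable versus not detectable RNA and objective 1.4.1, but not a log10 level. The stronger reading, that the RNA outcome as a whole yields no data, is wrong because the binary form has its own data and its own test.

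The impact is modest. This is half of one secondary outcome, in a subset, in a pilot that section 10.6 says is not powered for treatment differences and whose comparisons section 10.6.2 reserves for planning. No decision rule depends on it. It still deserves correction, because a pilot meant to document endpoint assessments should not list one that its described assay does not supply.

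The conclusion on the assay rests on the text alone. The 0.00 to 0.80 range rests on the assumptions in the working. It shows that the rule for negatives can determine the answer; it does not predict this trial's result.

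**What to change.** Choose one of two routes.

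- **Binary only.** Restrict 1.3.8, 10.2.2.7 and the matching sentence of 10.6.2 to detectable versus not detectable. This costs only wording, and the continuous outcome is lost.
- **Keep the continuous form.** State in 6.2.8 that the laboratory will release cycle-threshold or quantitative values, with the unit and the limit of detection. In 10.6.2, drop the normality-driven choice of a t-test. Specify a Wilcoxon rank sum test with non-detects tied at the lowest RNA rank and a correction for ties, so that negatives are neither excluded nor given an arbitrary number. A left-censored model is an optional addition. This costs a data-release request to the laboratory, which may be refused.

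If an expected share of non-detects is quoted for planning, give it as a range with its assumptions.

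Two small repairs belong in the same edit. First, define the subset: the kit list in 6.2.8 includes three swab sets without restriction. Second, correct the numbering in 10.6.2, which assigns secondary outcomes 5 to 7 to negative binomial regression as event rates. In section 10.2.2 number 7 is the RNA outcome. In section 1.3 the fifth to seventh items are hospital-free days and the two adverse event outcomes, so the numbers may come from that list.
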